### 5.2.3 Screening Criteria

There are no screening criteria other than the inclusion and exclusion criteria.

### 5.2.4 Inclusion Criteria

An individual must fulfill *all* of the following criteria in order to be eligible for trial enrollment:

- 1) Aged 10 to 18 yearsa, 19 to 64 yearsb, or  $\geq 65$  yearsc on the day of inclusion.
- 2) Informed consent form has been signed and dated by the subject, or assent form has been signed and dated by the subject and informed consent form has been signed and dated by the parent/guardian.
- 3) Subject or subject and parent/guardian able to attend all scheduled visits and to comply with all study procedures.

### 5.2.5 Exclusion Criteria

An individual fulfilling *any* of the following criteria is to be excluded from trial enrollment:

- 1) Subject is pregnant, or lactating, or of childbearing potential (to be considered of non-childbearing potential, a female must be pre-menarche or post-menopausal for at least 1 year, surgically sterile, or using an effective method of contraception or abstinence from at least 4 weeks prior to vaccination until at least 4 weeks after vaccinationd).
- 2) Participation at the time of study enrollment (or in the 4 weeks preceding the study vaccination) or planned participation during the present study period in another clinical trial investigating a vaccine, drug, medical device, or medical procedure.
- 3) Received any vaccine in the 4 weeks preceding the trial vaccination or planned receipt of any vaccine between V01 and V02. For influenza vaccine only, defer if received in the 14-day period prior to enrollment or scheduled to receive in the 14-day period after enrollment.
- 4) Known or suspected receipt of a tetanus toxoid, reduced diphtheria toxoid and acellular pertussis (Tdap) vaccine, or Tdap-containing vaccine at any point in time, or receipt of a tetanus and diphtheria-containing vaccine in the preceding 5 years.
- 5) Receipt of immune globulins, blood or blood-derived products in the past 3 months.

---

a “10 to 18 years” means from the day of the 10th birthday to the day before the 19th birthday

b “19 to 64 years” means from the day of the 19th birthday to the day before the 65th birthday

c “ $\geq 65$  years” means from the day of the 65th birthday or older

d For pre-menarche females, the young female subjects will declare by themselves if they have not yet started menstruation. If a young female subject reaches menarche during the study, then she is to be considered as a woman of childbearing potential from that time forward.

- 6) Known or suspected congenital or acquired immunodeficiency, immunosuppressive therapy such as anti-cancer chemotherapy or radiation therapy within the preceding 6 months, or long-term systemic corticosteroids therapy (prednisone or equivalent for more than 2 consecutive weeks within the past 3 months).
- 7) History of diphtheria, tetanus, or pertussis infection (confirmed either serologically or microbiologically).
- 8) Known or suspected systemic hypersensitivity to any of the vaccine components or history of life-threatening reaction to the study vaccine or a vaccine containing the same substancesa.
- 9) Laboratory-confirmed / self-reported thrombocytopenia or bleeding disorder contraindicating IM vaccination.
- 10) Bleeding disorder or receipt of anticoagulants in the 3 weeks preceding inclusion, contraindicating intramuscular vaccination.
- 11) History of encephalopathy (e.g., coma, decreased level of consciousness, or prolonged seizures) not attributable to another identifiable cause within 7 days of administration of a previous dose of diphtheria and tetanus toxoids and pertussis (DTP), or diphtheria and tetanus toxoids and acellular pertussis (DTaP) vaccine.
- 12) Deprived of freedom by an administrative or court order, or in an emergency setting, or hospitalized involuntarily.
- 13) Current alcohol abuse or drug addiction.
- 14) Chronic illness that, in the opinion of the investigator, is at a stage where it might interfere with trial conduct or completion.
- 15) Moderate or severe acute illness/infection (according to Investigator judgment) on the day of vaccination or febrile illness (temperature  $\geq 100.4^{\circ}\text{F}$ ). A prospective subject should not be included in the study until the condition has resolved or the febrile event has subsided.
- 16) Identified as an Investigator or employee of the Investigator or study center with direct involvement in the proposed study, or identified as an immediate family member (i.e., parent, spouse, natural or adopted child) of the Investigator or employee with direct involvement in the proposed study.

If the subject has a primary physician who is not the Investigator, the site—with the subject's consent—must make a reasonable and timely attempt to contact the primary physician to inform him/her of the subject's participation in the study. In addition, the site should ask the primary physician to verify exclusion criteria relating to medical history and previous therapies (such as receipt of previous vaccines, blood products, or immunosuppressive therapies). If contact with the subject's primary physician is unsuccessful, the subject may still be enrolled in the study so long as the Investigator considers the subject eligible to participate (i.e., the subject meets all inclusion criteria and does not meet any exclusion criteria).

---

a The components of SP0173 and comparator products are listed in [Section 6.1](#) and in the Investigator's Brochure.

### 5.2.6 Medical History

Prior to enrollment, subjects will be assessed for pre-existing conditions and illnesses, both past and ongoing. Any such conditions will be documented in the source document. Significant medical history (reported as diagnosis) including conditions for which the subject is or has been followed by a physician or conditions that could resume during the course of the study or lead to an SAE or to a repetitive outpatient care will be collected in the CRF. The significant medical history section of the CRF contains a core list of body systems and disorders that could be used to prompt comprehensive reporting, as well as space for the reporting of specific conditions and illnesses.

For each condition, the data collected will be limited to:

- Diagnosis (this is preferable to reporting signs and symptoms)
- Presence or absence of the condition at enrollment

The reporting of signs and symptoms is strongly discouraged.

Dates, medications, and body systems are not to be recorded, and the information collected will not be coded. Its purpose is to assist in the later interpretation of safety data collected during the trial.

### 5.2.7 Contraindications for Subsequent Vaccinations

Not applicable since only one dose of vaccine will be administered in this trial.

### 5.2.8 Conditions for Withdrawal

Subjects/Parents/Guardians will be informed that they have the right to withdraw themselves or their child from the trial at any time. A subject may be withdrawn from the study:

- In any situation where, in the opinion of the Investigator, continuation in the study would not be in the best interest of the subject due to safety concerns (withdrawal) without the subject's permission
- At the request of the subject (drop out)

The following will result in automatic withdrawal or exclusion of a subject from the study:

- Significant non-compliance with the protocol, based on the Investigator's judgment

The reason for a withdrawal or dropout should be clearly documented in the source documents and on the CRF.

The Investigator must determine whether voluntary withdrawal is due to safety concerns (in which case, the reason for discontinuation will be noted as "SAE" or "other AE" as appropriate) or for another reason.

Withdrawn subjects will not be replaced.

### 5.2.9 Lost to Follow-up Procedures

In the case of subjects who fail to return for a follow-up examination, documented reasonable effort (i.e., documented telephone calls and certified mail) should be undertaken to locate or recall them, or at least to determine their health status while fully respecting their rights. These efforts should be documented in the CRF and in the source documents.

### 5.2.10 Classification of Subjects Who Discontinue the Trial

For any subject who discontinues the trial prior to completion, the most significant reason for early termination will be checked in the CRF. Reasons are listed below from the most significant to the least significant (refer to the CRF completion guidelines for additional details and examples):

- **Serious adverse event:** To be used when a subject drops out of or is withdrawn from the study by the Investigator because of the occurrence of an SAE, as defined in [Section 9.3.1.1](#).
- **Other adverse event:** To be used when a subject drops out of or is withdrawn from the study by the Investigator because of the occurrence of an AE other than an SAE, as defined in [Section 9.3.1.1](#).
- **Non-compliance with protocol:** To be used when the Investigator withdraws a subject from the study because of failure to follow the protocol including when it is retrospectively discovered that a subject did not fulfill the eligibility criteria. The Investigator will provide a comment as to the specific cause of non-compliance.
- **Lost to follow-up:** To be used when the Investigator withdraws a subject from the study because of failure to establish contact, as outlined in [Section 5.2.9](#). The Investigator will provide documentation that contact was attempted (i.e., return of unsigned certified letter receipt).
- **Voluntary withdrawal not due to an adverse event:** To be used when a subject drops out of the study for any reason other than those listed above.

### 5.2.11 Follow-up of Discontinuations

The site should complete all scheduled safety follow-ups and contact any subject who has prematurely terminated the trial because of an SAE, other type of AE, non-compliance with the protocol, or loss of eligibility, including definite contraindications.

For subjects where the reason for early termination was lost to follow-up or if the subject withdrew informed consent and specified that they do not want to be contacted again and it is documented in the source document, the site will not attempt to obtain further safety information.

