### 5.1.3 Trial Plan

Eligible subjects will be identified and enrolled at each research center. Initially, enrollment will be restricted to the subjects in the adult age group (19–64 years of age). Enrollment of adolescent and older adult subjects is planned subsequent to a satisfactory review of safety data from V01 through V02 post-vaccination for the adult age group.

Each subject and/or subjects' parent/guardian must sign and date the ICF (and assent form for subjects under the age of legal majority [according to state regulation]) before any procedure or treatment associated with the study is performed.

Subjects will receive one injection of either SP0173 vaccine, Adacel®, or BOOSTRIX® on D0. Each subject will be asked to provide a blood sample (10–20 mL/bleeda) to be collected before vaccine injection at V01 (D0) and at V02 (30 days [ $\pm$  14 daysb] after injection).

All subjects and/or subjects' parent/guardian will be asked to record solicited injection site reactions and solicited systemic reactions that occur for 7 days after the injection and unsolicited AEs that occur from V01(D0) through V02 (D30). SAEs will be collected throughout the study period from D0 through D180 after vaccination. MAAEs will be collected throughout the study from V01 through V02 (as part of the collection of unsolicited AEs) and from V02 through D180 (as MAAEs).

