## 12.5 Determination of Sample Size and Power Calculation

Although there are no statistically powered hypotheses in this study, the overall study cohort (N=1350) will provide a probability of approximately 93% of observing any AE with a true incidence of 0.2%. For each formulation (N=225), there is a probability of approximately 95% of observing any AE with a true incidence of 1.3%, and a probability of approximately 36% of observing any AE with a true incidence of 0.2%.

Assuming a drop-out rate of approximately 10%, a total of 67 evaluable subjects per group is anticipated.

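### Protocol 5.2.11 bars further safety contact once a subject is terminated as lost to follow-up, so a subject closed out after an unreachable V02 is not tried at the scheduled D180 call

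*Protocol*

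**What the plan says.** Three consecutive sections of the protocol govern a subject who stops attending.

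- **5.2.9 (Lost to Follow-up Procedures).** When a subject does not come back, the site has to search, and even an incomplete search should establish how the subject is: "documented reasonable effort (i.e., documented telephone calls and certified mail) should be undertaken to locate or recall them, or at least to determine their health".
- **5.2.10 (Classification).** The lost-to-follow-up category applies when the Investigator "withdraws a subject from the study because of failure to establish contact, as outlined in" 5.2.9. Proof is required: "The Investigator will provide documentation that contact was attempted (i.e., return of unsigned certified letter receipt").
- **5.2.11 (Follow-up of Discontinuations).** Subjects who stop because of an SAE, another AE, non-compliance or loss of eligibility keep all their scheduled safety follow-up. A second paragraph names two classes that do not. One is subjects who withdrew consent and asked for no further contact. The other is introduced by "For subjects where the reason for early termination was lost to follow-up". For both, "the site will not attempt to obtain further safety information".

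Against this stands the collection plan in 5.1.3: "SAEs will be collected throughout the study period from D0 through D180 after vaccination". SAEs to 6 months, and MAAEs from V02 to 6 months, are named endpoints in 9.3.1.2. After the D8 call only two contacts are scheduled: V02 at D30 to D44, and Telephone Call 2 at D180 (+14 days).

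**The concern.** The rule treats a subject who could not be found in the same way as one who asked to be left alone. Only the second has given a reason not to be called.

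Telephone Call 2 needs no visit and comes months after V02. Someone in hospital, ill or away around D44 may answer by then. Failure to respond around V02 can itself be a consequence of a serious event, so the missing information may depend on the outcome being counted.

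Protocol 5.1.2 describes this as the first human study of these formulations, and safety is one of its two descriptive objectives. With 225 subjects per formulation, a single unseen SAE is visible in the reported percentage.

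**Working it through.** **1. Which subjects are affected.** Reading 5.2.9 to 5.2.11 in order:

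- Misses V02 but is reached by telephone or mail: not lost to follow-up. Nothing in the protocol cancels the D180 call.
- Misses V02 and the calls and certified mail fail: may be terminated as lost. The protocol gives no minimum number of attempts and no earliest date for this. If it is done soon after the V02 window, 5.2.11 then rules out the D180 attempt.
- Withdraws voluntarily, not because of an AE, without refusing contact: a category in 5.2.10, but in neither list in 5.2.11.

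**2. The gap in time.** From V02 to D180 is 180 − 44 = 136 days to 180 − 30 = 150 days, about 4.5 to 5 months.

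**3. How the loss enters the analysis.** The safety analysis set is all vaccinated subjects (Protocol 12.2.2, SAP 5.2.3). Missing safety data are not replaced (Protocol 12.3.1, SAP 5.3.1). SAEs and MAAEs are reported as percentages of subjects (SAP Table 5.1). For solicited reactions, SAP 4.4.1.1.3 removes subjects with no non-missing record from the analysis of that endpoint. No matching rule, and no person-time method, is given for SAEs or MAAEs. If the full safety set is the denominator, each unseen event lowers the reported figure for a vaccine group by 1/225 = 0.44 percentage points.

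**4. The plan's own detection figures.** Protocol 12.5 says "the overall study cohort (N=1350) will provide a probability of approximately 93% of observing any AE with a true incidence of 0.2" percent. With P(at least one event) = 1 − (1 − p)^N:

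- N = 1350, p = 0.002: 1 − 0.998^1350 = 93.3% (stated: about 93%).
- N = 225, p = 0.013: 1 − 0.987^225 = 94.7% (stated: about 95%).
- N = 225, p = 0.002: 1 − 0.998^225 = 36.3% (stated: about 36%).
- Evaluable per group and age stratum: 75 × 0.90 = 67.5 (stated: 67).

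All four reproduce.

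**5. Illustration of lost numbers.** No lost-to-follow-up rate is given. I assume that 1% to 10% of subjects have no 6-month data. The upper end is the plan's all-cause drop-out: 10% of 1350 = 135 subjects, and 10% of 225 = 22.5 per vaccine group.

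| | None lost | 1% lost | 10% lost |
|---|---|---|---|
| Overall, 0.2% event | 93.3% (N = 1350) | 93.1% (N = 1336) | 91.2% (N = 1215) |
| Per formulation, 1.3% event | 94.7% (N = 225) | 94.5% (N = 222) | 92.9% (N = 202) |
| Per formulation, 0.2% event | 36.3% (N = 225) | 35.9% (N = 222) | 33.3% (N = 202) |

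The loss of numbers is small. The table assumes that lost subjects have the same event rate as the rest, so it says nothing about bias.

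**The case against.** The strongest reply is that the protocol already searches for these subjects. Section 5.2.9 sets the least aim of the search as "or at least to determine their health status while fully respecting their rights", and 5.2.10 demands documentary proof before the category is used. There are other routes to an SAE as well:

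- The D8 call asks about SAEs, and staff keep calling until contact is made.
- Subjects are told to notify the site of any SAE.
- SAE ranks above lost to follow-up as a termination reason.
- Section 5.2.11 stops active attempts only; a site that learns of an SAE during participation must still report it under Section 10.

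The rule also applies alike to all six randomised groups under observer-blind assessment, in a study that tests no hypotheses. Nothing in the documents suggests that loss would differ by group.

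Much of this stands, and it rules out three readings that a reader might infer:

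- **That missing V02 alone forfeits the D180 call.** It does not; contact must first have failed.
- **That lost subjects are dropped from the analysis.** They remain in the safety set, and what was recorded before loss is analysed. Only later events are missing.
- **That a hospitalised or deceased subject necessarily goes unrecorded.** That happens only if the search and the other routes all fail.

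What the reply does not supply is a second attempt. The search in 5.2.9 follows the missed visit. The D8 call comes before V02. Self-notification and passive reporting depend on someone else acting. None of them replaces a scheduled call months later to a person who never declined it. Equal loss across groups would not remove a downward bias in each group's own percentage, and those percentages are what this descriptive study reports.

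**Conclusion.** The point holds in a limited form. Section 5.2.11 states an explicit bar, and the timing of a declaration of loss is left open. Together they allow a vaccinated subject who could not be reached after V02 to be closed out without the D180 attempt. Voluntary withdrawals who did not refuse contact are assigned to neither list.

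The direction of any bias in SAE and MAAE percentages is downward. This rests on two conditions: the safety set is the denominator, and some lost subjects had later events that no other route captured. The size cannot be calculated. The 10% in Protocol 12.5 covers drop-out for any cause and should not be read as a lost-to-follow-up rate; it is a ceiling only within that assumption. At that ceiling the chance of detecting a 0.2% event falls by about 2 points overall (93.3% to 91.2%) and 3 points per formulation (36.3% to 33.3%). The case for change rests on possible event-dependent missingness and on how cheap the remedy is. It does not rest on lost precision.

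**What to change.** Reword Protocol 5.2.11 so that the no-contact rule applies only to subjects who withdrew consent and asked not to be contacted. For every other vaccinated subject, including those lost to follow-up and voluntary withdrawals who did not refuse contact, attempt the scheduled Telephone Call 2 at D180 (+14 days), ask about SAEs and MAAEs, and record the outcome even when the attempt fails.

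The cost is a protocol amendment, which would need IEC/IRB approval if classed as substantial under 5.4, and some site time. At the assumed drop-out, at most about 135 attempts over about 20 sites is 135/20, or roughly 7 per site. The call is already in the schedule, so no new procedure is added.

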### 5.2.12 Follow-up and Reporting of Pregnancies

Pregnancy is an exclusion criterion for enrollment in this study, but a subject could potentially become pregnant during her participation. In case of pregnancy and if study vaccine has been administered, the subject will not be discontinued from the trial and will be followed for safety assessment (and may be followed for immunogenicity assessment, if applicable).

All pregnancy cases should be reported if they occurred during the study. To report the pregnancy case, the Investigator must fill out a Pregnancy Reporting Form in the electronic data capture (EDC) system and send it to the Sponsor within 1 month of identifying a pregnancy case.

Study staff must then maintain contact with the subject to obtain information about the outcome—i.e., details about the delivery and the newborn, or about pregnancy termination—and must update the electronic Pregnancy Reporting Form. This information should be provided to the Sponsor within 1 month of delivery.

Pregnancy itself is not considered an AE, but any complications during pregnancy are to be considered as AEs, and in some cases could be considered SAEs. Spontaneous abortions, fetal death, stillbirth, and congenital anomalies reported in the baby are always considered as SAEs, and the information should be provided to the Global Pharmacovigilance (GPV) Department regardless of when the SAE occurs (e.g., even after the end of the trial).

### 5.3 Safety Emergency Call

If, as per the Investigator's judgment, a subject experiences a medical emergency, the Investigator may contact the Sponsor's Responsible Medical Officer (RMO) for advice on trial related medical question or problem. If the RMO is not available, then the Investigator may contact the Call Center—available 24 hours a day, 7 days a week—that will forward all safety emergency calls to the appropriate primary or back-up Sanofi Pasteur contact, as needed. The toll-free contact information for the Call Center is provided in the OG.

This process does not replace the need to report an SAE. The investigator is still required to follow the protocol defined process for reporting SAEs to GPV (Please refer to [Section 10](#)).

In case of emergency code-breaking, the Investigator is required to follow the code-breaking procedures described in [Section 6.4](#).

### 5.4 Modification of the Trial and Protocol

Any amendments to this trial plan and protocol must be discussed with and approved by the Sponsor. If agreement is reached concerning the need for an amendment, it will be produced in writing by the Sponsor, and the amended version of the protocol will replace the earlier version. All substantial amendments (e.g., that affect the conduct of the trial or the safety of subjects) require IEC/IRB approval and must also be forwarded to regulatory authorities.

An administrative amendment to a protocol is one that modifies some administrative or logistical aspect of the trial but does not affect its design or objectives or have an impact on the subjects' safety. Regulatory authorities need only be notified about administrative changes. Administrative changes do not require IRB approval; however, the IRB must be notified whenever one is made. The Investigator is responsible for ensuring that changes to an approved trial, during the period for which IEC/IRB approval has already been given, are not initiated without IEC/IRB review and approval, except to eliminate apparent immediate hazards to subjects.

